5.6.1.1.6 Endocrine Events

Subjects should be carefully monitored for signs and symptoms of endocrine events (such as adrenal insufficiency, hypophysitis, hyperthyroidism, hypothyroidism). If symptoms (such as hypotension or arrhythmia) indicate possible new or worsening cardiac abnormalities, additional testing and/or a cardiology consultation should be considered. All attempts should be made to rule out other causes such as brain metastases, sepsis and/or infection. An endocrinology consultation is recommended.

Thyroid disorders can occur at any time during treatment. Monitor patients for changes in thyroid function (at the start of treatment, periodically during treatment, and as indicated based on clinical evaluation) and for clinical signs and symptoms of thyroid disorders.

Guidelines regarding management and dose reduction for endocrine events considered to be related to study treatment by the investigator are provided in [Table 10](#) and [Table 19](#).

For Type 1 diabetes mellitus (if new onset, including diabetic ketoacidosis [DKA]) or \geq Grade 3 Hyperglycemia, if associated with ketosis (ketonuria) or metabolic acidosis (DKA)

- Insulin replacement therapy is recommended for Type 1 diabetes mellitus and for Grade 3-4 hyperglycemia associated with metabolic acidosis or ketonuria.
- Evaluate patients with serum glucose and a metabolic panel, urine ketones, glycosylated hemoglobin, and C-peptide.

Table 19 Management and Dose Modification Guidelines for Endocrine AEs

CTCAE Grade	Adverse Event Management	Action and Dose Modification
Grade 1 or 2	
 Monitor thyroid function or other hormonal level tests and serum chemistries more frequently until returned to baseline values If hypophysitis or other symptomatic endocrinopathy (other than hypo- or hyperthyroidism) is considered, pituitary gland imaging should be considered (MRIs with gadolinium and selective cuts of the pituitary can show enlargement or heterogeneity and confirm the diagnosis). For Grade 2 hypophysitis or other symptomatic endocrinopathy other than hypo- or hyperthyroidism, treat with prednisone 40 mg p.o. or equivalent per day. When symptoms improve to grade 1 or less, initiate steroid taper over no less than 4 weeks. Replacement of appropriate hormones may be required as the steroid dose is tapered. Thyroid hormone and/or steroid replacement therapy to manage adrenal insufficiency. In hyperthyroidism, non-selective beta-blockers (e.g. propranolol) are suggested as initial therapy. In hypothyroidism, thyroid hormone replacement therapy, with levothyroxine or liothyronine, is indicated per standard of care. Consultation with an endocrinologist may be considered. 	
 Continue study treatment Interrupt pembrolizumab for Grade 2 events other than hypo- or hyperthyroidism (treatment may be continued while treatment for \leqGrade 2 thyroid disorder is initiated)
Symptomatic pan-hypopituitarism OR Grade 3-4	
 Consider Endocrinology consultation Rule out infection and sepsis with appropriate cultures and imaging. Treat with an initial dose of methylprednisolone 1 to 2 mg/kg intravenously followed by oral prednisone 1 to 2 mg/kg per day. When symptoms improve to Grade 1 or less, steroid taper should be started and continued over no less than 4 weeks. Replacement of appropriate hormones may be required as the steroid dose is tapered. Hypophysitis with clinically significant adrenal insufficiency and hypotension, dehydration, and electrolyte abnormalities (such as hyponatremia and hyperkalemia) constitutes adrenal crisis. Hospitalization, endocrine consultation, and intravenous methylprednisolone should be initiated. 	
 Interrupt pembrolizumab until AE resolves to grade \leq1 Restart pembrolizumab. If 2 interruptions of pembrolizumab are clinically indicated, permanently discontinue study pembrolizumab NOTE: Interrupt or permanently discontinue pembrolizumab is at the discretion of the investigator or treating physician. NOTE: pembrolizumab may be continued for Grade 3-4 hypothyroidism if thyroid replacement is initiated.
Abbreviation: CTCAE = Common Terminology Criteria for Adverse Events Note: Hyperglycemia (\geq Grade 3) requiring an increase in the dose of, or initiation of insulin or oral therapy can occur with dabrafenib. Monitor serum glucose levels as clinically appropriate during treatment with dabrafenib in subjects with pre-existing diabetes or hyperglycemia. Advise patients to report symptoms of severe hyperglycemia such as excessive thirst or any increase in the volume or frequency of urination.		

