Type 1 diabetes mellitus (T1DM) or Hyperglycemia See also Section 5.6.1.1.6	Newly onset T1DM or Grade 3 or 4 hyperglycemia associated with evidence of β -cell failure	Withhold	
 Initiate insulin replacement therapy for participants with T1DM Administer anti-hyperglycemic in participants with hyperglycemia 	
 Monitor participants for hyperglycemia or other signs and symptoms of diabetes.
Hypophysitis See also Table 19	Grade 2	Withhold	
 Administer corticosteroids and initiate hormonal replacements as clinically indicated. 	
 Monitor for signs and symptoms of hypophysitis (including hypopituitarism and adrenal insufficiency)
	Grade 3 or 4	Withhold or permanently discontinue ¹		
Hyperthyroidism See also Section 5.6.1.1.6	Grade 2	Continue	
 Treat with non-selective beta-blockers (eg, propranolol) or thionamides as appropriate 	
 Monitor for signs and symptoms of thyroid disorders.
	Grade 3 or 4	Withhold or permanently discontinue ¹		

Immune-related AEs	Toxicity grade or conditions (CTCAEv4.0)	Action taken to pembrolizumab	irAE management with corticosteroid and/or other therapies	Monitor and follow-up
Hypothyroidism See also Section 5.6.1.1.6	Grade 2-4	Continue	
 Initiate thyroid replacement hormones (eg, levothyroxine or liothyronine) per standard of care 	
 Monitor for signs and symptoms of thyroid disorders.
Nephritis and Renal dysfunction See also Table 23	Grade 2	Withhold	
 Administer corticosteroids (prednisone 1-2 mg/kg or equivalent) followed by taper. 	
 Monitor changes of renal function
	Grade 3 or 4	Permanently discontinue		
Myocarditis See also Section 5.6.1.1.12	Grade 1 or 2	Withhold	
 Based on severity of AE administer corticosteroids 	
 Ensure adequate evaluation to confirm etiology and/or exclude other causes
	Grade 3 or 4	Permanently discontinue		

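### The Grade 3-4 steroid bullet in Table 19 drops the thyroid exclusion that the same table applies at Grade 2, so it does not match the Table 10 thyroid rows, and no text says which table governs

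*Combined protocol and SAP*

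**What the plan says.** Section 5.6.1.1.6 introduces its guidance with "Guidelines regarding management and dose reduction for endocrine events considered to be related to study treatment by the investigator are provided in" Tables 10 and 19, naming both without ranking them.

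In Table 19, the steroid bullet of the Grade 1 or 2 row is limited by event: "For Grade 2 hypophysitis or other symptomatic endocrinopathy other than hypo- or hyperthyroidism, treat with prednisone 40 mg p.o. or equivalent per day". The same row covers thyroid disease separately. For overactivity it states: "In hyperthyroidism, non-selective beta-blockers (e.g. propranolol) are suggested as initial therapy". For underactivity it gives levothyroxine or liothyronine.

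The next row covers symptomatic pan-hypopituitarism or any Grade 3-4 event. Its steroid bullet has no limit by event: "Treat with an initial dose of methylprednisolone 1 to 2 mg/kg intravenously followed by oral prednisone 1 to 2 mg/kg per day". A taper over no less than 4 weeks follows once symptoms reach Grade 1 or less. The action column of that row adds: "NOTE: pembrolizumab may be continued for Grade 3-4 hypothyroidism if thyroid replacement is initiated".

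In Table 10 (Section 5.2.1.2.1), the hyperthyroidism row, which includes Grade 3 or 4, says: "Treat with non-selective beta-blockers (eg, propranolol) or thionamides as appropriate". The hypothyroidism row, Grades 2 to 4, says: "Initiate thyroid replacement hormones (eg, levothyroxine or liothyronine) per standard of care". Neither lists a corticosteroid. The hypophysitis row does.

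**The concern.** A site managing a Grade 3-4 thyroid event related to pembrolizumab is sent to two tables that do not say the same thing. If it follows the Table 19 row to the letter, the subject receives a high-dose steroid course that Table 19 withholds from thyroid events one grade lower and that the Table 10 thyroid rows do not list. The row also has no beta-blocker bullet, so a site that reads only that row for severe hyperthyroidism meets steroids and no thyroid-specific treatment for it.

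Section 8.2.1 has Part 3 subjects who stay on the triplet after unblinding continue under these guidelines, and subjects in Parts 4 and 5 also receive pembrolizumab. The number still on the drug is not stated, and Section 5.2.5 stops it at 24 months.

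**Working it through.** The plan gives no figure to reproduce here. The check is a comparison of texts.

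**1. Do thyroid events fall in the Grade 3-4 row?** Yes. Section 5.6.1.1.6 names hyper- and hypothyroidism among its endocrine events, the row is defined by grade, and its own note ("NOTE: pembrolizumab may be continued for Grade 3-4 hypothyroidism if thyroid replacement is initiated") would be pointless if severe hypothyroidism lay outside it.

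**2. What does each place direct?**

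| Event | Table 19 | Table 10 thyroid rows |
|---|---|---|
| Grade 2 thyroid | Excluded from prednisone 40 mg/day; beta-blocker or thyroid hormone | Beta-blocker/thionamide or thyroid hormone; no steroid listed |
| Grade 3-4 hyperthyroidism | Methylprednisolone, then prednisone, 1-2 mg/kg; no beta-blocker bullet | Beta-blocker or thionamide; no steroid listed |
| Grade 3-4 hypothyroidism | Same steroid bullet; hormone replacement may be needed during the taper; pembrolizumab may continue with thyroid replacement | Thyroid hormone; pembrolizumab continues; no steroid listed |

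The Grade 1 or 2 row of Table 19 sets thyroid disease apart three times: for pituitary imaging, for steroids and for interrupting pembrolizumab. The Grade 3-4 steroid bullet never does.

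There is also a smaller mismatch. Table 19 restarts pembrolizumab at Grade 1 or less. The Table 10 endocrinopathy note allows Grade 2 or less once the event is controlled.

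**3. Does any text rank the tables?** No.
- Section 5.2.1.2.1 points to Section 5.6 for steroid use in specific events, and Section 5.6.1 says to use the algorithm for the combination or the single agent. Both lean towards Table 19, and if it governs, the unlimited bullet stands.
- Section 5.6.1 also sends sites back to Table 10.
- Table 10 names Table 19 for the pituitary event ("Hypophysitis See also Table 19") but sends its thyroid rows to Section 5.6.1.1.6 as a whole. This hints that the steroid bullet was meant for hypophysitis, without saying so.
- For Grade 3 hepatic events, Table 10 defers to Table 30 for detailed management. The thyroid rows have no such instruction.

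**4. Illustrative dose.** Body weight and taper shape are assumptions.
- Oral dose = weight × 1 to 2 mg/kg. At 70 kg: 70 to 140 mg/day. Over 50 to 100 kg: 50 to 200 mg/day.
- Linear 28-day taper to zero = 28 × starting dose / 2. At 70 kg: 28 × 70 / 2 = 980 mg to 28 × 140 / 2 = 1,960 mg. Over 50 to 100 kg: 28 × 50 / 2 = 700 mg to 28 × 200 / 2 = 2,800 mg. Full-dose days before the taper would add to this.

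**The case against.** The strongest reply is that the row is plainly about pituitary and adrenal disease. Its label opens with pan-hypopituitarism, its hormone replacement is tied to the steroid taper, and its last management bullet describes adrenal crisis. Letting pembrolizumab continue in severe hypothyroidism also sits oddly with a high-dose steroid course. That is probably what was intended. But the row applies by grade and names a thyroid event, so the text does not deliver the intent.

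Three stronger readings are tempting, and the documents do not support them.
- *Table 10 forbids steroids for thyroid events.* Its thyroid rows are silent and do not prohibit them. Its general instruction 3 calls for IV and then oral steroid in severe immune-related events, without saying whether the thyroid rows override it. Table 10 is therefore not fully explicit either.
- *The protocol leaves severe hyperthyroidism without a beta-blocker, or severe hypothyroidism without hormone.* Section 5.6.1.1.6 cites Table 10, which lists these treatments at Grade 3-4, and the Table 19 row itself says hormone replacement may be required.
- *Sites will give the steroids.* Section 5.6.1.1.6 recommends endocrinology consultation, and the row says to consider it. Section 5.6.1 leaves supportive care to investigator judgment, Section 5.6.1.1.3 calls its text general guidance, and Section 5.6.1.3 has immune-related events of Grade 2 or higher discussed immediately with the sponsor.

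Exposure may also be small. Amendment 4, which dealt with operation after the Part 3 final analysis, dates from May 2018, and the current version from December 2019. With a 24-month limit, few Part 3 subjects may remain on pembrolizumab, although actual dates are not given.

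**Conclusion.** The point holds as a defect in the wording of one bullet. Table 19 applies a thyroid exclusion at Grade 2 and drops it at Grade 3-4. Followed as written, the bullet directs a 1-2 mg/kg steroid course for severe thyroid events that the Table 10 thyroid rows do not list, and nothing says which table prevails. The safeguards lower the chance that a subject is treated this way, but they do not settle which instruction applies.

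Confidence is high on the wording gap. The dose figures rest on assumed weights and an assumed linear taper and only illustrate scale. No thyroid event rate and no count of subjects still on pembrolizumab is given, so expected harm cannot be stated. The correction is worth making at the next amendment because it restores a distinction the protocol already draws and costs almost nothing.

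**What to change.** Make two edits in the Grade 3-4 row of Table 19.

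1. Limit the steroid bullet to *symptomatic pan-hypopituitarism, hypophysitis or other symptomatic endocrinopathy other than hypo- or hyperthyroidism*.
2. Add: *For Grade 3-4 hypo- or hyperthyroidism, follow the Table 10 thyroid rows and the Table 10 endocrinopathy restart note; use steroids only if separately clinically indicated.*

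The second edit settles which table governs thyroid events, brings in the beta-blocker and thionamide guidance, and removes the restart mismatch for these events.

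Two further clarifications are optional: the same treatment for type 1 diabetes and hyperglycemia, which the bullet does not exempt either, and a sentence in Table 10 saying that its thyroid rows override general instruction 3.

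The cost is amendment wording only, with no new data, visits or subjects.

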5.6.1.1.7 Vision Changes

Subjects should be carefully monitored for signs and symptoms of vision changes (such as uveitis, iritis, retinal pigment epithelial detachment [RPED], and Retinal Vein Occlusion [RVO]). Symptoms may include (but not limited to): blurred vision, diffuse erythema and a prominent blush on the sclerae, dryness of the eyes, pain, or photophobia. All attempts should be made to rule out other causes such as metastatic disease, infection or other ocular disease (e.g. glaucoma or cataracts).

Episodes of visual changes have been observed in subjects receiving dabrafenib, trametinib or the combination of both therapies, as well as in subjects receiving pembrolizumab. In addition, ocular AEs are known to be related to trametinib. The causal relationship between a change in vision and the study treatment should be carefully explored and an ophthalmologist should be consulted. However, if the visual changes are clearly unrelated to study treatment (e.g., allergic conjunctivitis), then close monitoring is acceptable and it may be reasonable to defer ophthalmic examination. Special attention should be given to retinal (e.g., RPED) or retinovascular abnormalities (e.g., branch or central RVO). For events of visual changes regardless of severity for which an ophthalmic examination is conducted, a blood sample for PK analysis must be drawn as close as possible to the time of the event.

Guidelines regarding management and dose reduction for visual changes and/or ophthalmic examination findings considered to be related to study treatment are provided in [Table 20](#).

Management guidelines for Retinal Pigment Epithelial Detachment (RPED) are provided separately in [Table 21](#).

Table 20 Management and Dose Modification Guidelines for Visual Changes and/or Ophthalmic Examination Findings

CTCAE Grade ^a	Adverse Event Management	Action and Dose Modification
Grade 1	
 Consult ophthalmologist within 7 days of onset (preferably prior to next dose of pembrolizumab) Treat with topical steroids such as 1% prednisolone acetate suspension and iridocyclitics as appropriate. 	
 If dilated fundoscopic examination cannot be performed within 7 days of onset, interrupt trametinib until RPED and RVO can be excluded by retinal specialist/ophthalmologist. If RPED and RVO excluded, continue (or restart) trametinib at same dose level If RPED suspected or diagnosed: see RPED dose modification table below; report as SAE. If RVO diagnosed: Permanently discontinue trametinib and report as SAE. Uveitis: Interrupt pembrolizumab and consider interrupting dabrafenib until symptoms resolve and exam shows resolution Non-RPED/RVO: Discontinue pembrolizumab if symptoms persist despite treatment with topical and systemic immunosuppressive therapy.
Grade 2 and Grade 3	
 Consult ophthalmologist immediately Treat with topical steroids such as 1% prednisolone acetate suspension and iridocyclitics as appropriate. For Grade 3 visual changes, consider treatment with systemic corticosteroids such as prednisone at a dose of 1 to 2 mg/kg per day as appropriate. When symptoms improve to ≤Grade 1, steroid taper should be started and continued over no less than 4 weeks. 	
 Interrupt pembrolizumab and trametinib until signs and symptoms resolve to baseline If RPED and RVO excluded, restart trametinib at same dose level If RPED diagnosed, see RPED dose modification table below; report as SAE. If RVO diagnosed: Permanently discontinue trametinib and report as SAE Non-RPED/RVO: Discontinue pembrolizumab if symptoms persist despite treatment with topical and systemic immunosuppressive therapy. Uveitis: Interrupt pembrolizumab and dabrafenib, treat with topical steroids until symptoms resolve and exam shows resolution
Grade 4	
 Consult ophthalmologist immediately Report as SAE Management as per Grade 3 above 	
 Interrupt trametinib Permanently discontinue pembrolizumab If RPED and RVO excluded, may consider restarting trametinib at same or reduced dose after discussion with study medical monitor If RVO or RPED diagnosed, permanently discontinue trametinib
Abbreviations: RPED = Retinal Pigment Epithelial Detachment; CTCAE = Common Terminology Criteria for Adverse Events; RVO = retinal vein occlusion; SAE = serious adverse event a. Refers to CTCAE Version 4.0 'Eye disorders – Other, specify		

Table 21 Recommended Dose Modifications for Trametinib for Retinal Pigment Epithelial Detachments (RPED)

CTCAE Grade	Action and Dose Modification
Grade 1 RPED ^a (Asymptomatic; clinical or diagnostic observations only)	
Continue treatment with retinal evaluation monthly until resolution. If RPED worsens follow instructions below
Grade 2-3 RPED ^a (Symptomatic with mild to moderate decrease in visual acuity; limiting instrumental ADL)	
Interrupt trametinibRetinal evaluation monthlyIf improved to \leq Grade 1, restart trametinib at lower dose (reduced by 0.5 mg) or discontinue in patients taking trametinib 1 mg daily

a) Refers to CTCAE Version 4.0 'Retinopathy'

5.6.1.1.8 Pneumonitis

Subjects should be carefully monitored for signs and symptoms of pneumonitis, interstitial lung disease, or acute interstitial pneumonitis. If symptoms (such as chest pain and/or tightness or dyspnea) indicate possible new or worsening cardiac abnormalities, additional testing and/or a cardiology consultation should be considered. All attempts should be made to rule out other causes such as metastatic disease, bacterial or viral infection.

Pneumonitis has been observed in subjects receiving trametinib, as well as in subjects receiving pembrolizumab. To reduce the risk of pneumonitis, subjects will be monitored closely for symptoms, evaluated with imaging and functional tests. Dose modification and supportive care guidelines for pneumonitis are described in [Table 10](#) and [Table 22](#).

It is important that patients with a suspected diagnosis of pneumonitis be managed as per the guidance below until treatment-related pneumonitis is excluded. Treatment of both a potential infectious etiology and pneumonitis in parallel may be warranted. Management of the treatment of suspected pneumonitis with steroid treatment should not be delayed for a therapeutic trial of antibiotics. If an alternative diagnosis is established, the patient does not require management as below; however the AE should be reported regardless of etiology.

Table 22 Management and Dose Modification Guidelines for Pneumonitis

CTCAE Grade	Adverse Event Management	Action and Dose Modification
Grade 1	
 CT scan (high-resolution with lung windows) recommended, with serial imaging to monitor for resolution or progression Clinical evaluation and laboratory work-up for infection Monitoring of oxygenation via pulse-oximetry recommended Consultation of pulmonologist recommended 	
 Continue study treatment at current dose
Grade 2	
 CT scan (high-resolution with lung windows) Consider frequent Chest X-ray for monitoring Clinical evaluation and laboratory work-up for infection Consult pulmonologist, consider Infectious Disease consultation Conduct in-person evaluation approximately twice per week Bronchoscopy with biopsy and/or BAL recommended Treat with systemic corticosteroids at a dose of 1 to 2 mg/kg/day prednisone or equivalent. When symptoms improve to Grade 1 or less, steroid taper (if systemic corticosteroids initiated) should be started and continued over no less than 4 weeks. 	
 Interrupt study all treatment until recovery to grade ≤ 1 Treatment with pembrolizumab may be resumed if the event improves to \leq Grade 1 within 12 weeks and corticosteroids have been reduced to the equivalent of methylprednisolone 10 mg PO daily or less. Repeat chest imaging monthly as clinically indicated. Treatment with dabrafenib and trametinib at one dose level reduction may be resumed if the event improves to \leq Grade 1 within 4 weeks; escalation to previous dose level after 4 weeks may be possible after discussion with sponsor If no recovery to grade ≤ 1 within 4 weeks or second episode of Grade 2 or higher pneumonitis on re-challenge, permanently discontinue all study treatment
Grade 3	
 Hospitalize patient CT scan (high-resolution with lung windows) Clinical evaluation and laboratory work-up for infection Consult pulmonologist Bronchoscopy with biopsy and/or BAL if possible Immediate treatment with intravenous steroids (methylprednisolone 125 mg). When symptoms improve to \leq Grade 1, a high dose oral steroid (prednisone 1 to 2 mg/kg once per day or dexamethasone 4 mg every 4 hours) taper should be started and continued over no less than 4 weeks. If IV steroids followed by high dose oral steroids does not reduce initial symptoms within 48 to 72 hours, consider alternate therapy (treat with additional anti-inflammatory measures). Discontinue alternate therapy upon symptom relief and initiate a prolonged steroid taper over 45 to 60 days. If symptoms worsening during steroid reduction, initiate a retapering of steroids starting at a higher dose of 80 or 100 mg followed by a more prolonged taper and consider alternate therapy as needed. 	
 Permanently discontinue pembrolizumab Interrupt dabrafenib and trametinib until recovery to \leq Grade 1 After consultation with Sponsor, dabrafenib and trametinib may be restarted reduced by one dose level If no recovery to grade ≤ 1 within 4 weeks, permanently discontinue dabrafenib and trametinib
Grade 4	
 Same as grade 3 	
 Permanently discontinue all study treatment

Abbreviations: BAL= bronchoalveolar lavage; CT = computed tomography; CTCAE = Common Terminology Criteria for Adverse Events

